3.0 Procedures

As described in our Implementation Core*, three core products will be developed in Year 1: 1) a Construct Assessment Tool; 2) a Barrier Busters Tool; and 3) a Program Intelligence Portal (Portal). These products will be made available online for use by MOVE! teams in all VHA facilities. Much of the work has already been done on the Construct Assessment and Barrier Busters Tools. Most of our tool development effort in the first year will be devoted to developing the Portal, which will draw on advanced methods for visually displaying data in a way that has meaning for local teams. For example, users might be interested in seeing geographic displays (e.g., choropleth maps) to visually display where MOVE! participants are coming from compared to non-participants, or longitudinal graphs of engagement and weight outcomes over time. In partnership with OABI, our team will develop a Portal for MOVE! that utilizes next-generation analytic and data visualization tools (e.g., Pyramid Analytics)¹⁵⁶ available through the VA eQuality Measures (eQM) platform. The Portal will be developed using principles of user-centered design that will help to ensure it truly meets the needs of local teams.¹⁵⁷⁻¹⁵⁹ Each of the three products developed in the first year have been specifically chosen to address high-priority gaps. ***In fact, NCP is so eager to embrace these tools we are making them available online to all sites in Year 2*** and will evaluate their effectiveness via interrupted time-series analyses (described below).

Posting products online is likely to achieve only incremental benefits, because local or individual constraints will preclude accessing and using them effectively. Thus, LEAP will be employed to provide intensive support using methods that make it feasible for scaling up to all sites; in fact, we plan to randomize 48 sites (plus three pilot sites) through the course of the project (see Figure 5 below), with the remaining sites acting as controls.

LEAP, as described in the Implementation Core, will be adapted to work with VAMC teams to implement *New MOVE!*. Findings from prior work with a quality collaborative revealed the importance of open communication, relationship building, methods training, monitoring performance, and facilitating team-

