3.1 Study Design

Our goal is to evaluate outcomes for all VAMCs nationwide. For Aim 1, because our NCP partners want to quickly disseminate the core products by posting them online and providing short orientations on national calls, we will use an interrupted time series analysis to assess primary, secondary, and tertiary outcomes before and after dissemination of the products among sites who do not participate in LEAP. Outcome assessments will rely on administrative data available through the Corporate Data Warehouse (CDW). Our team has extensive experience working with MOVE! program data and linking to other utilization and diagnosis data.^{141,142,145-147}

For Aim 2, in years 2-3 we will randomly assign sites to LEAP, six sites at a time. At the beginning of each quarter, sites not included in the pilot and not randomized in previous quarters will be characterized by tertile of performance with respect to aggregate visits (our primary implementation outcome). Two sites will be randomly selected from each tertile of performance to initiate LEAP.

Thus, each cohort of sites will comprise two high performing sites (a key “ingredient” for the LEAP sessions), two “learner sites” and two sites that have moderate performance. This will provide a forum where the more successful sites can “mentor” sites who are further behind. By the end of FY18, 48 sites will have participated in LEAP, plus three pilot sites in FY16. The final three months of follow-up for the last cohort will occur in FY19Q1.

[figure not shown]

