3.2 Key Variables & Analyses

The primary outcome will be VAMC-level aggregated number of MOVE! visits accrued within a six-month analysis period among candidates for MOVE! who live within 40 miles of the VAMC: an implementation outcome with respect to reach.¹⁶⁰ The secondary outcome will be average percentage weight loss by patients at each VAMC at six months after a baseline MOVE! visit. Tertiary outcomes will include: 1) the proportion of patients who have at least 12 MOVE! visits within 12 months (a specified goal in the new CPGs); and 2) the proportion of patients who achieved at least 5% weight loss at six months.

For Aim 1, in addition to developing the three core products, we will evaluate their impact after they are disseminated to VAMCs in FY17 through interrupted time series analyses using administrative program data. Data prior to launch of these products (FY17 Q1) will provide “before” data. “After” data will come from sites not randomized to receive the more intensive intervention (see Aim 2) and up to the randomization time for sites randomized to LEAP. Analytic models will be similar to that of Aim 2, except the primary exposure variable will be an indicator for the period after dissemination of the three core products .

To determine effectiveness of LEAP (Aim 2), we will use a generalized linear mixed-effects model with visit counts and log link for primary outcome, percent weight loss for secondary outcome, and whether at least 12 visits in 12 months were made (1/0) and logit link for tertiary outcomes. Each model will include site as random intercepts and two indicators for tertiles as fixed effects. The primary exposure variable will be the binary time-dependent exposure variable indicating the intervention quarter for the site, i.e., a variable indicating the quarter at or beyond when the site is randomized to initiate LEAP. For each outcome, the

Figure 5: Project Activities and Stepped-wedge Trial Design

Key: Gray = Participation in Learn. Engage. Act. Program (LEAP)

parameter estimate of this exposure variable will allow testing for the effectiveness of LEAP and summarize the LEAP effect expressed as rate ratio for primary outcome, difference in percent weight change for secondary outcome, and odds ratio for tertiary outcome. The model can include other variables (e.g., quarter and participant covariates).

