Power considerations. Across all sites, there will be about 22,080 MOVE! participants (20 participants per closed MOVE! cohort X 1 cohort per quarter X 8 quarters X 147 sites, with 48 sites randomized in steps to LEAP and 99 not randomized). Our previous work showed an average of 4 visits during the 6 months of follow-up and 6% completing at least 8 visits.¹⁴² We assume the minimum detectable and meaningful difference in rates during LEAP in comparison to the control period to be 7 vs. 5 visits (corresponding to a rate ratio of 1.4 and assuming a bit higher rate in control group than the number observed in the preliminary data due to implementation of tools across all sites) and percent of patients with at least 12 visits in 12 months as 10% vs. 7% (corresponding to an odds ratio of 1.48). For power considerations, the design assumes randomization of 6 sites (2 sites per tertile) to LEAP every quarter over 8 quarters starting at Q1 of FY17, and one unexposed quarter, while 3 sites are piloted (Q4 of FY16), no differential effect of LEAP across the tertiles, that 48 sites will be randomized to LEAP (rather than all VAMCs), and a within-site correlation of 0.1. The proposed design will have 99% power to detect the odds ratio of 1.4 or higher and 91% power to detect an odds ratio of 1.48 or higher with a two-sided 0.05 test.

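### Aim 1 tests a launch that reaches every site in one quarter with a model whose only stated random effect is site, so any quarter-to-quarter variation shared by the sites is left out of the H1 standard error

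*Combined protocol and SAP*

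**What the plan says.** Section 3.1 (Study Design) describes Aim 1 as a before-and-after evaluation: "we will use an interrupted time series analysis to assess primary, secondary, and tertiary outcomes before and after dissemination of the products". The products are not staggered. Section 3.0 (Procedures) says "we are making them available online to all sites in Year 2", and section 3.2 (Key Variables & Analyses) dates the launch: "Data prior to launch of these products (FY17 Q1) will provide" the before period.

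For the model, section 3.2 refers to Aim 2: "Analytic models will be similar to that of Aim 2, except the primary exposure variable will be an indicator for the period after dissemination". The Aim 2 structure is "Each model will include site as random intercepts and two indicators for tertiles as fixed effects". Calendar time is optional and its form is not given: "The model can include other variables (e.g., quarter and participant covariates".

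The after-launch "data will come from sites not randomized to receive the more intensive intervention (see Aim 2) and up to the randomization time" of the sites that go on to LEAP. The power paragraph counts "147 sites, with 48 sites randomized in steps to LEAP and 99 not randomized".

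For Aim 1 the document gives no calendar-quarter random effect, no serial-correlation structure, no number of before quarters, and no power or standard error.

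**The concern.** In Aim 2, exposure differs between sites within a quarter, so sites are real replicates and calendar time can be separated from LEAP. In Aim 1 the exposure has one value for all sites in any given quarter. Season, national policy or a change in recording that moves all VAMCs together in a quarter then goes straight into the estimated product effect, and adding sites does not average it out. A model with only a site intercept treats that movement as independent noise, to be divided by about 147 sites.

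This is a separate question from adjusting for a secular trend. A correctly specified trend removes drift but leaves the shared deviations around it. Site-clustered robust errors do not help either, because the deviations are common to all clusters. What is at stake is the interval and p-value for H1: ordinary national fluctuation could be reported as a benefit of the products.

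**Working it through.** The document states no Aim 1 power or standard error, so there is no plan figure to reproduce. The check is whether a site-only model gives the right standard error.

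**Inputs from the document.** One launch quarter for all sites; 147 sites; six sites leaving for LEAP in each of 8 quarters. After-launch site-quarters: 141 + 135 + 129 + 123 + 117 + 111 + 105 + 99 = 960.

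**Assumptions (the document gives no values).** 8 before quarters; site-by-quarter SD s_e = 0.25 on the log scale; shared quarter SD s_q from 0 to 0.10; a two-sided 5% test, which is stated for Aim 2 and carried over to H1.

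**Step 1. Can a fixed quarter factor absorb the shocks?** The post-launch indicator is the sum of the eight after-quarter dummies. The 16 quarter dummies plus the indicator make 17 columns of rank 16, so the H1 effect is not estimable.

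**Step 2. True against reported standard error.** Ignoring the departure of LEAP sites, a quarterly mean over N = 147 sites has true variance s_q² + s_e²/N. The site-only model reports about (s_e² + s_q²)/N. The ratio of standard errors is

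R = √[(s_q² + s_e²/N) / ((s_e² + s_q²)/N)], and type I error is P(|Z| > 1.96/R).

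With s_e²/N = 0.0625/147 = 0.000425:

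| s_q | True variance | Reported variance | R | Type I error |
|---|---|---|---|---|
| 0 | 0.000425 | 0.000425 | 1.00 | 5% |
| 0.01 | 0.000525 | 0.000426 | 1.11 | 8% |
| 0.02 | 0.000825 | 0.000428 | 1.39 | 16% |
| 0.05 | 0.002925 | 0.000442 | 2.57 | 45% |
| 0.10 | 0.010425 | 0.000493 | 4.60 | 67% |

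**Step 3. Simulation with the LEAP sites leaving and a linear trend fitted.**
- With s_e = 0.25 and 400 runs per setting, rejection under no effect was 5.0%, 13.8%, 45.5% and 67.0% at s_q = 0, 0.02, 0.05 and 0.10. The model SE stayed at 0.021-0.023, while the actual SD of the estimate was 0.022, 0.028, 0.059 and 0.103.
- Separate code with Poisson counts, s_e = 0.2 and 1,000 runs gave 4.8%, 17.6%, 48.1% and 69.6%.
- In that code, at s_q = 0.02, 0.05 and 0.10, 4 before quarters gave 16.0%, 43.6% and 65.9%, and 12 gave 17.1%, 45.2% and 69.2%.

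**Step 4. Sensitivity to which sites count.** Section 3.1 limits Aim 1 to sites that do not take part in LEAP, while section 3.2 adds LEAP sites up to randomisation. With N = 99, s_e²/N = 0.0625/99 = 0.000631, and the Step 2 formula gives R = 1.08, 1.27, 2.18 and 3.81 and type I error of 7%, 12%, 37% and 61% at s_q = 0.01, 0.02, 0.05 and 0.10. The conclusion does not change.

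**Step 5. What restores the size.** Taking the quarter as the unit, with a trend and t on (quarters − 3) degrees of freedom, gave 4.3-6.0% under independent shocks (s_e = 0.2). With lag-1 correlation of 0.5 and s_q = 0.05 it rejected 12.8%. When six-month windows overlap, independent-error quarter-level inference rejected 11-14% at s_q = 0.05-0.10. Newey-West errors on 16 quarterly points rejected 14-16% even with independent shocks.

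**Step 6. Cost in precision.** For a step plus a linear trend over 8 + 8 quarters, the step variance is 1.012 × (s_q² + s_e²/147). This gives SE = √(1.012 × 0.002925) = 0.054 at s_q = 0.05 and √(1.012 × 0.010425) = 0.103 at 0.10. The power paragraph's rise from 4 observed visits to 5 assumed under the products is a ratio of 1.25, with log 0.223. That is 0.223/0.054 = 4.1 SEs in the first case and 0.223/0.103 = 2.2 in the second.

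**The case against.** The strongest reply is that the plan has not committed to the faulty model. The Aim 1 models are only said to be similar to those of Aim 2, other variables may be added, and the analysis is called an interrupted time series, which is a time-based method. The document is also an excerpt that points to an outside page for more analysis detail, and that page could not be consulted. This stands in part: a different final model is possible. But the sentence carries the Aim 2 structure over with the exposure as its only stated exception, and no fixed quarter term allowed under the optional wording repairs the error. A categorical term removes the H1 effect, and a trend or seasonal term leaves the remaining shared deviations in place.

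The second reply is that the size is assumed. That stands. No shared SD is given, and at 1% the inflation is small.

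The third is that H1 is a non-randomised evaluation of online tools. That stands too, and it limits the severity. A reader might infer that LEAP effectiveness is also undermined. The document does not support that, because LEAP starts are staggered and H2 does not rest on a single launch date.

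**Conclusion.** The concern holds for H1. As written, the Aim 1 model gives too small a standard error whenever sites share any quarter-to-quarter variation, with or without a trend. The direction does not depend on the assumed values; the size does. With 8 before and 8 after quarters and a site-by-quarter SD of 0.25, type I error runs from about 8% (shared SD 1%) through 14-16% (2%) and about 45% (5%) to 67% (10%).

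A reader might infer that the H1 interval and p-value are certain to be badly wrong. The document does not support that: it gives no shared SD, the test holds near 5% if there is no shared variation, and its wording leaves some latitude over the final model. With H2 untouched and the cure cheap, this is a should-fix.

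**What to change.** In the Aim 1 models:
- Add a calendar-quarter random effect crossed with site, with a serial-correlation structure such as AR(1). Alternatively, analyse non-overlapping six-month periods, since the primary outcome accrues over six months and windows evaluated each quarter would share data.
- Include a time trend, and seasonal terms if enough before quarters are extracted. State how many before quarters will be used.
- Test the post-dissemination term against a t distribution with degrees of freedom based on the number of periods.
- State that categorical quarter effects cannot be used for Aim 1, and do not rely on Newey-West errors on a short quarterly series.
- Reconcile sections 3.1 and 3.2 on which sites supply after-launch data.

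The cost is a few sentences and an extra variance structure on administrative data already planned for, plus a wider H1 interval. At a shared SD of 5% the SE is about 0.055-0.06 and a ratio of 1.25 stays detectable. At 10% the SE is about 0.10-0.13 and power for 1.25 is limited: about 52% with independent shocks, and 43% once seasonal terms are added. That loss reflects how much information one launch date carries.

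### The patient-level Aim 2 models name only a site random intercept, so site-by-quarter variation would be missing from the LEAP standard error; the effect on type I error ranges from slight to material, depending on two inputs the text leaves open

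*Combined protocol and SAP*

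**What the plan says.** All the model text is in section 3.2 (Key Variables & Analyses).

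- **Random effects:** "Each model will include site as random intercepts and two indicators for tertiles as fixed effects". No other random effect is named, nor any robust variance or small-sample correction.
- **Exposure:** "a variable indicating the quarter at or beyond when the site is randomized to initiate LEAP". It varies by quarter within site and stays on once started.
- **Tertiary outcomes:** the model is for "whether at least 12 visits in 12 months were made (1/0) and logit link for tertiary outcomes", which is a patient-level binary model. At least 5% weight loss is the other tertiary outcome.
- **Secondary outcome:** "average percentage weight loss by patients at each VAMC at six months after a baseline MOVE! visit". This is worded as a site average, and the unit of analysis is not stated.
- **Calendar time:** optional. "The model can include other variables (e.g., quarter and participant covariates".
- **Power considerations:** "a within-site correlation of 0.1", with no split into within-quarter and between-quarter parts and no scale named. The paragraph also gives one closed cohort of 20 per site per quarter, 48 stepped and 99 non-randomized sites, 10% versus 7% for the 12-visit outcome, and 91% power at an odds ratio of 1.48.

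Section 3.0 describes the sites outside LEAP as controls. The opening page calls the document an excerpt of the funded proposal and refers to an outside page for further design and analysis detail.

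**The concern.** With a site intercept alone, two patients in the same quarterly cohort are taken to be no more alike than two patients who joined that site two years apart. The programme itself makes this doubtful. Each quarter is a separate closed group, and section 1.0 expects New MOVE! to work through cohesive groups with one consistent coach. Such influences can differ from cohort to cohort within a site.

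LEAP is estimated largely from changes across quarters within sites, so cohort-to-cohort noise feeds straight into the estimate. A binary model has no free residual variance to absorb it. Fixed quarter effects, if included, remove only what is common to all sites. The LEAP interval can then be too narrow, and chance variation could be reported as a LEAP effect. The 12-visit outcome is a guideline target with its own power claim, and Aim 3 is meant to inform scaling-up.

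**Working it through.** **Inputs from Power considerations.** 8 steps of 6 sites plus one unexposed quarter (I = 48, T = 9); m = 20 per site-quarter; risks 7% and 10%; correlation ρ = 0.1; two-sided 0.05.

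**Assumed.** r, the between-quarter correlation divided by the within-quarter one: 1, 0.9, 0.8 or 0.5. The documents give no value, and r = 1 is what a site-only intercept implies. The calculation is a linear approximation with total variance v = 0.07 × 0.93 = 0.0651 and fixed quarter effects.

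**Step 1: reproduce the 91%.** The standard stepped-wedge variance is

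Var = Iσ²(σ² + Tτ²) / [(IU − W)σ² + (U² + ITU − TW − IV)τ²],

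where U = 216 is the number of exposed site-quarters, W = 7,344 the sum of squared quarter totals and V = 1,224 the sum of squared site totals.

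- σ² = 0.0651 × 0.9 / 20 = 0.00293; τ² = 0.0651 × 0.1 = 0.00651.
- IU − W = 3,024; U² + ITU − TW − IV = 15,120.
- Var = 0.00865 / (8.86 + 98.43) = 0.0000806; SE = 0.00898.
- Power = Φ(0.03/0.00898 − 1.96) = 91.6%.

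So the stated 91% is what one obtains from the 48 sites with no site-by-quarter variation.

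**Step 2: add site-by-quarter variation, total correlation held at 0.1.** Now σ² = v × 0.9/20 + v × 0.1 × (1 − r) and τ² = v × 0.1 × r. At r = 0.8, σ² = 0.00423, τ² = 0.00521 and SE = 0.01065, so power with the term modelled is Φ(0.03/0.01065 − 1.96) = 80.4%.

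**Step 3: what the site-only model would report.** It fits one correlation, close to the average over all patient pairs in a site. With 180 patients there are 1,710 same-quarter and 14,400 other pairs. At r = 0.8 the average is 0.1 × (1,710 + 0.8 × 14,400)/16,110 = 0.082. The model SE is then 0.00903, against a true SE for that estimator of 0.01068: a ratio of 1.18. Type I error = 2[1 − Φ(1.96/1.18)], or about 9.7%.

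**Step 4: the scale of 0.1.** A logit-link mixed model may carry this correlation on the logit scale. The site variance is then (0.1/0.9) × π²/3 = 0.366. To first order the proportion-scale correlation at 7% is 0.0651 × 0.366 = 0.024; numerical integration gives about 0.026. Repeating steps 1 to 3 with 0.026:

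| 48 sites | r = 1 | 0.9 | 0.8 | 0.5 |
|---|---|---|---|---|
| Proportion scale: true/model SE | 1.00 | 1.10 | 1.18 | 1.40 |
| Type I error | 5.0% | 7.4% | 9.7% | 16.0% |
| Power with term modelled | 91.6% | 86.0% | 80.4% | 67.3% |
| Logit scale: true/model SE | 1.00 | 1.02 | 1.04 | 1.10 |
| Type I error | 5.0% | 5.5% | 6.0% | 7.4% |
| Power with term modelled | 92.0% | 91.0% | 90.2% | 88.6% |

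Both scales give about 92% power at r = 1, so the match to 91% does not show which was meant.

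**Step 5: with the 99 other sites (147 in all).** Type I error at r = 0.9, 0.8 and 0.5 is 7.3%, 9.5% and 15.4% (proportion scale) or about 5.5%, 5.9% and 7.1% (logit scale). More sites do not remove the problem. Power with the term modelled is 98.9%, 97.7% and 93.5% on the proportion scale, and above 99% on the logit scale.

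**Check against a logistic fit.** Simulated site-intercept logistic fits under the null (147 sites, 300 replicates) gave 6.3% at r = 1 and 13.7% at r = 0.8 on the proportion scale, and 6.7% at r = 1 and 9.0% at r = 0.5 on the logit scale. Monte Carlo error is about 2 points at 13.7%. The direction agrees, but the linear figures should not be read to the decimal.

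**The case against.** Four points can be made for the plan.

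**The driving quantity is not in the documents.** Every inflated figure needs r below 1, and nothing in the text supports a particular value. This stands: the point is an unprotected risk, not a demonstrated error rate.

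**The size depends on the scale of the 0.1.** This also stands. On the logit scale the inflation is small, and quoting only the proportion-scale figures would overstate both the defect and the cost of repair.

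**The text requires a site intercept; it does not forbid more.** It allows other variables, and the document is an excerpt that refers elsewhere for detail. This limits the claim to the supplied text. The optional terms given as examples, quarter and participant covariates, would not supply the missing site-by-quarter variance.

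**The power is safe if the 99 other sites enter as controls.** Correct: it stays at about 93% or more over the range examined. A reader might infer from the 67% that the trial is underpowered, but that holds only for 48 sites, the proportion scale and r = 0.5.

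A reader might also extend the point to the primary outcome, "VAMC-level aggregated number of MOVE! visits accrued within a six-month analysis period", analysed by a "generalized linear mixed-effects model with visit counts and log link for primary outcome". The documents do not support that. They state neither the count family nor whether six-month totals are rolling or follow closed cohorts, so no inflation can be established. Likewise, if weight loss is fitted to site-quarter means, the residual absorbs independent site-by-quarter variation.

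**Conclusion.** The point holds for the patient-level Aim 2 models as the supplied text describes them: at least 12 visits, at least 5% weight loss, and percent weight loss only if fitted to patients. As written, these models have no place for site-by-quarter variation, in a design where the exposure changes by quarter within site.

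For r from 0.9 down to 0.5, type I error with 48 sites runs from about 7% to 16% if 0.1 is a proportion-scale correlation and from about 5.5% to 7.5% if it is a logit-scale one. At r = 1 it is 5%. The figures rest on an assumed r, 20 patients per site-quarter and a linear approximation. The logit-scale conversion is specific to a 7% event rate, and applying 0.1 to the weight-loss outcome is a further assumption.

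The change should be made because it is cheap and guards against an error whose size the plan cannot rule out. The outcomes clearly affected are tertiary, and confidence in the size is moderate.

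**What to change.** For the patient-level models, add a random site-by-quarter effect, or use a site-robust variance with small-sample correction. Make quarter a required fixed effect, so that the new term captures only site-specific deviations. In simulated null logistic trials with r from 1 to 0.5, a marginal analogue of the first option (separate within- and between-quarter correlations) had type I error of 4.4% to 6.3%, and a bias-corrected site-robust variance 5.0% to 5.9%. Also state whether percent weight loss is fitted to patients or to site-quarter means.

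Restate the 91% power over a stated range of between-quarter correlation, naming the scale of the 0.1 and whether the 99 non-randomized sites enter. On 48 sites it becomes about 86%, 80% or 67% (proportion scale) or 91%, 90% or 89% (logit scale) at r = 0.9, 0.8 or 0.5. With the 99 sites it stays at about 93% or above.

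The cost is SAP wording and no new data. LEAP intervals widen by about 10% to 40% on the proportion scale or 2% to 10% on the logit scale over the assumed range, and hardly at all if there is no site-by-quarter variation.

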2.0 Rationale

Since its inception in 2006, MOVE! has enjoyed relative success. However, the high burden of overweight/obesity in VHA creates an urgency to strive for greater improvements in MOVE! effectiveness with respect to system-wide outcomes and to decrease the high variation in MOVE! program characteristics and outcomes across VAMCs. VAMCs report high annual rates (95%)^{143,153} of obesity screening and brief counseling,¹⁵³ which presents a key opportunity to engage Veteran who are candidates for MOVE!. Although VHA compares quite favorably in rates of individuals who initiate participation in a weight loss program – less than 6% initiate participation in weight loss programs in the general population,¹⁵⁴ while 10-12%¹⁴³ of MOVE! candidate Veterans do so – there is room for improvement.

Figure 4: Aggregate FY2014 MOVE! Group Visits per 100 Overweight/Obese Veterans Enrolled in Primary Care by VAMC

[figure not shown]

Figure 4 shows the wide variation in MOVE! group visit rates across VAMCs in FY2014. The highest-ranked VAMC reported more than 70 MOVE! group visits per 100 candidate Veterans. However, several VAMCs appear not to have a viable MOVE! group program, reporting fewer than 10 visits. One reason for high variation in aggregate visits may be variation in local organizational barriers. Our earlier work with three different lifestyle programs (MOVE!, TeleMOVE, and the Telephone Lifestyle Coaching (TLC) program) consistently revealed high variation in the

presence of key organizational barriers, which affects viability of MOVE! group programming. In a recent NCP call with 79 MOVE! Coordinators, **99% expressed willingness to participate in a program aimed at providing more intensive support to implement *New MOVE!*. This dramatically high level of interest speaks to the strong need for additional support to assist with implementation.**

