2.0 Implementation Strategy: LEAP (Learn. Engage. Act. Program) + Core Products

LEAP (Learn. Engage. Act. Program.) is the primary implementation strategy we are proposing to develop and use for the projects included in this proposal (with an abbreviated version being proposed for our QI project). LEAP, plus additional products we plan to develop, is depicted in Figure 2. Our implementation strategy begins with change triggered by new clinical practice guidelines (CPGs). We propose to support implementation of CPGs in local VAMC settings with our Core Products and LEAP. The embedded “wheels” at the center of the figure depict the interacting and mutually reinforcing role of high-priority CFIR constructs. The four key Process constructs (inner wheel) interact to overcome barriers related to constructs in the Inner Setting (outer wheel). LEAP will employ the “micro” strategies listed in Table 1 (next page) in a way that is tailored to the local Inner Setting. Teams at local sites will employ these strategies, guided by the Barrier Busters Tool (described below) and integrated with systems redesign approaches. We hypothesize that use of these strategies will lead to successful implementation of CPGs in VAMCs as reflected by improved implementation outcomes. Improved implementation will in turn lead to optimal patient outcomes – in the case of our PROVE QUERI projects, these outcomes will be the more personalized care encapsulated by the CPGs.

Figure 2: Implementation Strategy Framework

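### The primary Aim 2 count model allows no site-to-site variation in LEAP's effect, so if the effect does vary, the rate ratio's confidence interval is too narrow for the average across sites

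*Combined protocol and SAP*

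**What the plan says.** Section 3.2 (Key Variables & Analyses) specifies for the primary outcome a "generalized linear mixed-effects model with visit counts and log link for primary outcome". The random-effects structure is common to all Aim 2 outcomes: "Each model will include site as random intercepts and two indicators for tertiles as fixed effects". LEAP enters once: "The primary exposure variable will be the binary time-dependent exposure variable indicating the intervention quarter for the site". Inference rests on that term, since the "parameter estimate of this exposure variable will allow testing for the effectiveness of LEAP" and also gives the rate ratio. Further terms are optional and are covariates: "The model can include other variables (e.g., quarter and participant covariates").

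The count distribution and any dispersion term are not named. The document contains no random LEAP effect, LEAP-by-tertile term, cluster-robust standard error or permutation test. The power paragraph of section 3.2 assumes no difference in LEAP's effect across tertiles and is silent on variation between sites within a tertile. The implementation strategy section (2.0, LEAP + Core Products) says that LEAP will use its component strategies "in a way that is tailored to the local Inner Setting".

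**The concern.** A single fixed coefficient assumes that LEAP multiplies visits by the same factor at all 48 LEAP sites. With a locally tailored intervention, equal effects are a strong assumption. A site's deviation from the average effect starts at its crossover and lasts through all its LEAP quarters, so it does not average out over quarters. A random intercept shifts all of a site's quarters equally and cannot represent such a deviation. The tertile indicators cannot either. The standard error therefore draws on 216 LEAP site-quarters, although only 48 site effects are observed.

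At stake is the stated precision of the primary rate ratio. The model also gives no estimate of how much LEAP's effect varies, which bears on Aim 3's purpose of informing scale-up.

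**Working it through.** **Inputs from section 3.2.** 147 sites, of which 48 start LEAP six per quarter over 8 quarters and 99 never do; one unexposed quarter, so 9 quarters; 20 participants per site-quarter at 5 control visits each, so 100 visits; target effect "7 vs. 5 visits (corresponding to a rate ratio of 1.4"); two-sided 0.05.

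**Assumptions, because the document gives no figure.** The between-site SD of the log ratio, τ, is 0, 0.1, 0.2 or 0.3. Site-quarter variation beyond Poisson has a coefficient of variation (CV) of 0, 0.2 or 0.5. Sites are of equal size, counts are separate by quarter, and quarter effects are in the model.

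**Design quantities.** Remove site and quarter effects from the LEAP indicator.
- LEAP site-quarters: 6 × (8+7+…+1) = 216.
- Residual sum of squares: S = 216 − 6×204/9 − 36×204/147 + 216²/1323 = 216 − 136 − 49.96 + 35.27 = 65.31.
- A site with m LEAP quarters has weight w = (40/441)·m(9−m).
- K = Σw²/S² = (6×1968)/(6×120)² = 0.02278, since over m = 1 to 8 the sum of m(9−m) is 120 and the sum of its squares is 1968.

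**Formulas.** Let v = 1/100 + CV², the variance of a site-quarter log count.
- Reported SE = √(v/S)
- True SE = √(v/S + τ²K)
- Coverage = 2Φ(1.96 × reported/true) − 1

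**The plan's own figure.** The stated 99% power is printed for an odds ratio of 1.4. I read this as the rate ratio, because power for an odds ratio of 1.4 could not exceed the 91% given for 1.48. With Poisson variance and τ = 0, SE = √(0.01/65.31) = 0.0124 and log(1.4)/SE = 0.3365/0.0124 = 27, so power is above 99.9%. That is compatible with 99%, but power is saturated, so it is a weak check.

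**One case in full (CV 0.2, τ = 0.2).** v = 0.05. Reported SE = √(0.05/65.31) = 0.0277. True SE = √(0.000766 + 0.04×0.02278) = √0.001677 = 0.0409. Coverage = 2Φ(1.32) − 1 = 81.5%. Around 1.4, the reported interval is 1.33 to 1.48; one based on the true SE is 1.29 to 1.52.

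**All cases.**

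| CV | Reported SE | True SE, τ = 0.1 / 0.2 / 0.3 | Coverage (%) |
|---|---|---|---|
| 0 (Poisson) | 0.0124 | 0.0195 / 0.0326 / 0.0469 | 78.6 / 54.3 / 39.5 |
| 0.2 | 0.0277 | 0.0315 / 0.0409 / 0.0531 | 91.5 / 81.5 / 69.3 |
| 0.5 | 0.0631 | 0.0649 / 0.0699 / 0.0777 | 94.3 / 92.3 / 88.9 |

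At τ = 0, coverage is 95% in every row. A fitted dispersion term absorbs a little of the effect variation, so real coverage in the last two rows is slightly higher. A simulation with residual SD 0.25 and τ = 0.2 gave a mean reported SE of 0.031, an empirical SE of 0.044 and 84% coverage. The formulas give 0.031, 0.043 and 84% with v = 0.0625.

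**Cost in width at CV 0.2.** True/reported SE is 0.0315/0.0277 = 1.1, 0.0409/0.0277 = 1.5 and 0.0531/0.0277 = 1.9.

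**Power after the fix.** At the largest true SE in the table, 0.3365/0.0777 = 4.33 and Φ(4.33 − 1.96) = 99.1%.

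**Tertiary odds ratio** (20 patients per site-quarter, within-site correlation 0.1). At τ = 0.3 the reported SE is 0.0958 against a true 0.1058, and coverage is 92%. Weight loss was not computed.

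**The case against.** The strongest reply is that the defect is conditional and its size rests on assumed inputs. No between-site SD is given. Tailoring does not prove unequal effects and could even them out. Section 2.0 (Rationale) says "One reason for high variation in aggregate visits may be variation in local organizational barriers", but that concerns visit rates, and the site intercept absorbs differences in level. All of this stands: variation in effect is plausible, not shown.

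A reader might infer that the H2 test has a false-positive rate far above 0.05. The document does not support that as a general statement. If LEAP does nothing at any site, τ is 0 and this mechanism adds no error. Inflation needs an average ratio of exactly 1.0 with LEAP helping some sites and harming others. At τ = 0.2, Φ(log(0.9)/0.2) = 30% of sites would then lose more than 10% of their visits because of LEAP, and nothing in the document suggests this. Under-coverage at a ratio such as 1.4 needs no such null, so it is the fair form of the complaint.

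Four further points limit the size.
- The plan does not name Poisson, so the first row of the table is the worst case. With fitted dispersion and noisy site-quarters the loss is modest.
- The primary outcome accrues over six months, whereas the check uses separate quarterly counts.
- If the target is the average over these 147 sites only, the error rate at an average ratio of 1.0 and CV 0.2 falls from about 8.5, 18.5 and 31% to 7.5, 15 and 25%: smaller, but not removed.
- The document is an excerpt and points to an external analysis page that could not be consulted. A site random intercept is also a conventional stepped-wedge choice.

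None of these puts the missing variance component into the model as written.

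**Conclusion.** The point holds in conditional form. As specified, the primary count model understates the uncertainty of the average rate ratio whenever LEAP's effect differs between sites. For between-site SDs of 0.1, 0.2 and 0.3, coverage of the nominal 95% interval is about 79, 54 and 39% under Poisson variance. With fitted dispersion it is about 92, 82 and 70% at CV 0.2, and about 94, 92 and 89% at CV 0.5. These figures rest on the assumed SDs and dispersion, equal-size sites and quarterly counts.

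Three stronger readings go too far. The interval is not certainly too narrow, because the document does not establish that effects vary. The test is not inflated when LEAP has no effect at any site. And the Aim 2 outcomes are not all equally affected: the loss for the tertiary odds ratio is small, and weight loss was not assessed. Primary power is not in question. This is a worthwhile, inexpensive improvement to the analysis, and nothing here shows that the primary conclusion would be wrong.

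**What to change.** In section 3.2, do one of the following for the primary count model:
- Add a site-level random LEAP effect, allowed to correlate with the site intercept, and report the average rate ratio together with the between-site SD of the effect.
- Keep the random-intercept model with a dispersion term and use site-clustered standard errors with a small-sample correction. This also serves as the fallback if the first model does not converge.

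State which is primary, and apply the same choice to the other Aim 2 models for consistency.

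In simulations with an average ratio of 1.0 and CV 0.2, site-clustered standard errors gave 6 to 7% error. A random LEAP effect gave 5 to 6%, but it was tested in a linear mixed model on log counts; the correlated-slope count model itself was not simulated. At a ratio of 1.4 and an effect SD of 0.2, site clustering gave 94% coverage.

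The cost is a change of wording, one variance term or a different standard error, and no new data. The interval widens by a factor of about 1.1 to 1.9 at CV 0.2. The stated 99% power at a ratio of 1.4 is retained under the assumptions above.
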